#### **4. CHANGES IN THE PLANNED ANALYSIS OF THE STUDY**

All analyses described in this TSAP are in accordance with the statistical methods described in the CTP.

## **5. ENDPOINTS**

### **5.1 PRIMARY ENDPOINTS**

Primary endpoints are PK endpoints as defined in Section 5.5.1.1 of the CTP:

- $AUC_{0-tz}$  (area under the concentration-time curve of BI 655130 in plasma over the time interval from 0 to the last quantifiable data point)
- $C_{max}$  (maximum measured concentration of BI 655130 in plasma)

### **5.2 SECONDARY ENDPOINT**

#### **5.2.1 Key secondary endpoint**

Not applicable.

#### **5.2.2 Secondary endpoint**

Secondary endpoint is  $AUC_{0-\infty}$  (area under the concentration-time curve of BI 655130 in plasma over the time interval from 0 extrapolated to infinity).

### **5.3 FURTHER ENDPOINTS**

#### **5.3.2 Safety parameters**

**CTP:**

*Safety and tolerability of the investigational drug will be assessed based on:*

- *Adverse events (including clinically relevant findings from the physical examination)*
- *Safety laboratory tests*
- *12-lead ECG*
- *Continuous ECG monitoring*
- *Vital signs (blood pressure, pulse rate)*
- *Local tolerability*
- *Oral body temperature*

Local tolerability will be assessed as absence or presence of "swelling", "induration", "heat", "redness", "pain", or "other findings".

## **5.4 OTHER VARIABLES**

### **5.4.1 Demographic and other baseline characteristics**

**CTP:** *At screening, the medical examination will include demographics including height and body weight, smoking and alcohol history, relevant medical history and concomitant therapy [...].*

Age [years] will be determined as the difference between year of birth and year of informed consent.

BMI will be calculated as weight [kg] / (0.01 \* height [cm]).

### **5.4.2 Treatment compliance and treatment exposure**

Treatment compliance will not be analysed as a specific endpoint, cf. Section 4.3 of the CTP.

Treatment exposure is defined as the total dose of BI 655130 per subject.

Additionally, the duration of infusion per subject is calculated for the treatment group of subjects who receive BI 655130 intravenously.

## **6. GENERAL ANALYSIS DEFINITIONS**

### **6.1 TREATMENTS**

For basic study information on treatments to be administered, assignments of dose groups, and selection of doses, cf. Section 4 of the CTP.

Subjects were planned to be treated either with one single dose of

- as subcutaneous (SC) injection (exploratory reference treatment (ER))  
or
- as intravenous (IV) infusion (reference treatment (R))  
or
- as SC injection (test treatment (T)).

For statistical analysis of AEs, safety laboratory data and vital signs, the following analysis phases are defined for each subject:

Table 6.1: 1 Flow chart of analysis phases for statistical analyses of AEs, safety laboratory data and vital signs

Study analysis phase	Label	Start (inclusive)	End (exclusive)
Screening	Screening	Date of informed consent	Date/time of administration of study drug
On-treatment	BI SC, or BI IV or BI SC, respectively	Date/time of administration of study drug	0:00 AM on day after subject's trial termination date

CTR Section 15, Appendix 16.1.9.2.8.2 and Appendix 16.1.9.2.8.3 AE displays will present results for the on-treatment phase only.

In CTR Section 15 AE tables (but not in Appendix 16.1.9.2.8.2 and Appendix 16.1.9.2.8.3 AE tables), the following total will be provided in addition:

- "**Total on-trt BI**", defined as the total over all on-treatment phases involving BI 655130

CTR Appendix 16.1.9.2.8.1 displays will present results for the screening and on-treatment phases.

Additionally to the totals defined above, the following total will be provided in CTR Section 16.1.9.2.8.1 AE tables:

- "**Total**", defined as the total over all study phases (incl. screening and on-treatment).

More details on the technical implementation of these analyses are provided in the ADS Plan of this TSAP.

## **6.2        IMPORTANT PROTOCOL VIOLATIONS**

Consistency check listings (for identification of violations of time windows) and a list of protocol deviations (e.g. deviations in drug administration) will be provided to be discussed at the RPM/DBLM. At this meeting, each protocol deviation must be assessed to determine whether it is an IPV. For definition of IPVs, and for the process of identification of these, refer to the BI reference document "Protocol Violation Handling Definitions" (2).

If any IPVs are identified, they are to be summarised into categories and will be captured in the RPM/DBLM minutes via an accompanying Excel spreadsheet (3). The following table contains the categories which are considered to be IPVs in this trial. If the data show other IPVs, this table will be supplemented accordingly by the time of the RPM/DBLM.

IPVs will be summarised and listed.

Table 6.2: 1    Important protocol violations

Category / Code	Description
A	Entrance criteria not met
A1	Inclusion criteria violated
A2	Exclusion criteria violated
B	Informed consent
B1	Informed consent not available
B2	Informed consent too late
C	Trial medication and randomisation
C1	Incorrect trial medication taken
C3	Non-compliance
C5	Incorrect intake of trial medication
D	Concomitant medication
D1	Concomitant medication with the potential to affect the assessment of the trial medication
E	Missing data
	None 
G	Other trial specific important violations
G1	Certain violations of procedures used to measure primary PK data

Violations C1, C2, C5 and G1 can only be detected at the trial site.

 Missing visits, evaluations, and tests will be considered missing data, not PVs

Source: BI reference document "Protocol Violation Handling Definitions" [001-MCS-50-413\_RD-01] (2).

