#### **4.1.5 Blinding and procedures for unblinding**

No blinding will be performed because the treatments are distinguishable from each other. This Phase I trial will be handled in an open fashion throughout (that is, during the conduct, including data cleaning and preparation of the analysis). This is considered acceptable because the potential for bias seems to be low and does not outweigh practical considerations. PK samples will be labelled in such a way that treatment allocation cannot be derived by the analytical site.

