## 7.3 PLANNED ANALYSES

### 7.3.1 Primary analyses

The pharmacokinetic endpoints listed in [Section 5.5.1](#) will be calculated according to the BI Standard Operating Procedure (SOP) 'Standards and processes for analyses performed within Clinical Pharmacokinetics/Pharmacodynamics' ([001-MCS-36-472](#)).

Plasma concentration data and parameters of a subject will be included in the statistical pharmacokinetic (PK) analyses if they are not flagged for exclusion due to a protocol violation relevant to the evaluation of PK (to be decided no later than in Report Planning Meeting) or due to PK non-evaluability (as revealed during data analysis, based on the criteria specified below). Exclusion of a subject's data will be documented in the CTR.

A PK concentration or parameter will be considered as non-evaluable if, for example, the subject did not receive the complete assigned infusion or injection volume.

Relevant protocol violations may be

- Study drug not administered or wrong trial drug administered
- Incorrect dose of trial medication taken
- Missed/missing PK samples at important phases of PK disposition curve

The PK parameter analysis set (PKS) includes all subjects in the Treated Set (TS) who provide at least one primary or secondary PK parameter that was not excluded according to the description above. Thus, a subject will be included in the PKS, even if he contributes only one PK parameter value to the statistical assessment.

Relative bioavailability will be estimated by the ratios of the geometric means (test/reference) for the primary and secondary endpoints (see [5.5.1.1](#), [5.5.1.2](#)), and their two-sided 90% confidence intervals (CIs) will be provided.

To this end, the PK endpoints will be log transformed (natural logarithm) prior to fitting the ANOVA model (cf. [Section 7.1.3](#)). For each endpoint, the difference between the expected means for  $\log(T)-\log(R)$  will be estimated by the difference in the corresponding adjusted means (LeastSquares Means), and a two-sided 90% confidence interval based on the

Proprietary confidential information © 2017 Boehringer Ingelheim International GmbH or one or more of its affiliated companies

t-distribution will be computed. These quantities will then be back-transformed to the original scale to provide the point estimate and 90% CIs for each endpoint.

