### **6.3 SUBJECT SETS ANALYSED**

The following subject sets will be defined for statistical analysis:

- Treated set (TS):  
This subject set includes all subjects who received study drug.
- Pharmacokinetic parameter set (PKS):  
This subject set includes all subjects of the TS who provide at least one observation for at least one primary or secondary PK endpoint without important PVs with respect to the statistical evaluation of PK endpoints, as defined in Section 7.3.1 and Section 7.3.2 of the CTP.

The discussion of all exceptional cases and problems and the decisions on the allocation of subjects to analysis sets will be made at latest at the RPM/DBLM.

Table 6.3: 1 Subject sets analysed

Class of endpoint	Subject set	
	TS	PKS
Disposition	X	
Exposure	X	
IPVs	X	
Demographic/baseline endpoints	X	
Other safety parameters	X	
PK endpoints		X

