#### Exclusion of PK parameters

The ADS ADPP contains column variables APEXC and APEXCO indicating inclusion/exclusion (APEXC) of a PK parameter and an analysis flag comment (APEXCO). All analyses based on the PKS are based on PK parameter values which are not flagged for exclusion, i.e. with APEXC equal to "Included".

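### Does the SAP footnote that treats missing tests as non-violations override the protocol's rule on missing PK samples for AUC0-tz?

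*SAP*

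**What the plan says.** SAP 6.2 lists the categories of important protocol violation. Category E, missing data, has no entry, and its footnote reads "Missing visits, evaluations, and tests will be considered missing data, not PVs". The same table has category G1, for certain procedural violations affecting the primary PK data, and the list is open: "If the data show other IPVs, this table will be supplemented accordingly by the time of the RPM/DBLM".

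Protocol 7.3.1 gives examples of violations that may be relevant to the PK evaluation. One is "Missed/missing PK samples at important phases of PK disposition curve". The list is introduced permissively, and a concentration or parameter can also be left out as non-evaluable, a separate route. Any exclusion must be documented in the trial report.

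SAP 6.3 admits to the PK set treated subjects with at least one PK endpoint value "without important PVs with respect to the statistical evaluation of PK endpoints, as defined in Section 7.3.1 and Section 7.3.2 of the CTP". SAP 7.4 runs the primary analysis as laid down in protocol 7.1.3 and 7.3.1 and adds a parameter-level flag: "All analyses based on the PKS are based on PK parameter values which are not flagged for exclusion". SAP 4 states: "All analyses described in this TSAP are in accordance with the statistical methods described in the CTP".

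**The concern.** Taken alone, the footnote says a missed PK sample is never a protocol violation, and the protocol says it can be one. SAP 4 acknowledges no difference. Neither document says which phases of the curve count or when a shortened AUC0-tz should be dropped.

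The endpoint makes this worth checking. AUC0-tz is primary and runs only to each subject's last quantifiable sample, while planned sampling continues to Day 176. A subject who stops early contributes a short area. If it is kept, the SC/IV ratio falls when the subject is in the SC arm and rises when in the IV arm, and the residual variance grows. If it is removed, one observation is lost. With 12 subjects per arm, one such subject could be visible in the result. SAP 6.3 settles the matter late: "decisions on the allocation of subjects to analysis sets will be made at latest at the RPM/DBLM". Protocol 4.1.5 keeps the trial open during data cleaning, so the people deciding could know the treatment.

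**Working it through.** **1. Which text governs which decision**

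| Decision | Governing text | Role of footnote 1 |
|---|---|---|
| What is tabulated as an important violation | SAP 6.2, Table 6.2:1 | Applies |
| Who is in the PK set | SAP 6.3, referring to protocol 7.3.1 and 7.3.2 | Not mentioned |
| Which PK parameter values are analysed | SAP 7.4 flag; protocol 7.3.1 non-evaluability | Not mentioned |
| How missing PK data are handled | SAP 6.6 and protocol 7.4, citing the sponsor's PK SOP | Not mentioned |

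The datasets would differ only if the important violations in SAP 6.3 were read as Table 6.2:1 alone. That reading is possible but goes against the cross-reference in the same sentence. Even then, category G1, the option to extend the table and the parameter flag would each allow the exclusion.

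**2. The plan's own precision figures**

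Inputs from protocol 7.5: 12 per group, two-sided 90% CI, 95% coverage probability, gCV 15.6%, 12.7% and 7.17%. With σ = √ln(1+gCV²) and df = n₁+n₂−2:

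w = t(0.95, df) · σ · √(1/n₁+1/n₂) · √(χ²(0.95, df)/df), precision = exp(2w).

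For gCV 12.7%: σ = 0.1265, t = 1.717, χ² = 33.92, df = 22. So w = 1.717 × 0.1265 × 0.4082 × 1.2418 = 0.110, and precision is 1.246. The three rows give 1.310, 1.246 and 1.133, against 1.31, 1.25 and 1.13 in Table 7.5:1.

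**3. One truncated subject in 12**

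Protocol 1.2.5 reports half-lives of 20.4 to 33.9 days and calls them an estimate only; 25 days is an assumed middle value. Mono-exponential decline is also an assumption. The share of the area to Day 176 captured when sampling stops d days after dosing is

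f = [1−exp(−ln2·d/t½)] / [1−exp(−ln2·175/t½)],

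and the arm's geometric mean shifts by f^(1/12) − 1.

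| Last sample | Later PK visits missed | f (t½ 20.4 / 25 / 33.9) | Arm shift |
|---|---|---|---|
| Day 29 (d=28) | 8 | 0.615 / 0.544 / 0.448 | −4.0% / −4.9% / −6.5% |
| Day 57 (d=56) | 5 | 0.853 / 0.795 / 0.701 | −1.3% / −1.9% / −2.9% |
| Day 92 (d=91) | 3 | 0.957 / 0.927 / 0.869 | −0.4% / −0.6% / −1.2% |

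**4. Keep or exclude: effect on precision**

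Kept values: 200,000 simulated trials of 12 against 12, one subject shifted by ln f, 95th percentile of the half-width. Excluded: the formula in step 2 with 12 against 11, df 21.

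| gCV | Complete | Kept, Day 29 | Kept, Day 57 | Kept, Day 92 | Excluded |
|---|---|---|---|---|---|
| 12.7% | 1.246 | 1.32–1.41 | 1.255–1.287 | 1.247–1.253 | 1.254 |
| 15.6% | 1.310 | 1.37–1.46 | 1.32–1.35 | 1.31–1.32 | 1.320 |

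Coverage of the 90% interval stays at 90% to 92% when the value is kept.

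**5. Isolated gaps and an earlier stop**

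A one-compartment profile on the Flow Chart times, with assumed SC absorption rates of 0.15 to 0.3 per day, gives a change of under 2% in one subject's AUC0-tz when only the Day 15 sample is missing. With every sample from Day 29 onward missing, so that Day 22 is the last, the arm shift is −5.4% to −10.7%.

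**The case for a change.** The strongest argument for a change is that estimation is the stated aim, so the ratio and its interval are the result, and both can depend on an unwritten rule. The routes that would allow exclusion do not say when to use them. G1 covers certain violations without naming them, the flag records a decision without giving its basis, and the protocol's only example of non-evaluability is an incomplete dose. At Day 29, keeping or dropping one value moves precision from about 1.25 to as much as 1.41 at gCV 12.7%.

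Part of this stands. The wording is untidy and the visible documents contain no criterion. But the Day 29 case means missing all eight later PK visits. That is early withdrawal, for which protocol 3.3.5 allows replacement; protocol 6.1 allows missed visits to be rescheduled. At Day 57 or Day 92 the choice changes precision little. A fixed cut-off would not be clearly better. A day such as 92 can only be derived from an assumed decline, and protocol 1.2.5 reports target-mediated disposition. Whether a criterion is missing at all depends on the SOP, which SAP 6.6 and 7.4 already cite.

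**Conclusion.** No change follows. The footnote governs the tabulation of important violations, and the PK set follows protocol 7.3.1 through SAP 6.3 and 7.4. An analyst following the plan can exclude a badly truncated AUC0-tz and must document it. The undefined phases are a gap in detail that the cited SOP or the report planning meeting can fill sensibly. A sentence saying that the footnote does not override protocol 7.3.1 would be tidier, but it would not alter an analysis.

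The size is conditional on early loss of a subject, for which the documents give no rate. One subject in 12 shifts an arm by 4.0% to 6.5% at Day 29 and by at most 2.9% at Day 57 or 1.2% at Day 92. These figures rest on mono-exponential decline with the protocol's provisional half-lives and complete profiles to Day 176 for everyone else. Protocol 7.2 sets no acceptance range, so no pass or fail decision turns on the point. AUC0-∞ is analysed alongside as a second view, though for such a subject it would rely heavily on extrapolation.

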### **6.3 SUBJECT SETS ANALYSED**

The following subject sets will be defined for statistical analysis:

- Treated set (TS):  
This subject set includes all subjects who received study drug.
- Pharmacokinetic parameter set (PKS):  
This subject set includes all subjects of the TS who provide at least one observation for at least one primary or secondary PK endpoint without important PVs with respect to the statistical evaluation of PK endpoints, as defined in Section 7.3.1 and Section 7.3.2 of the CTP.

The discussion of all exceptional cases and problems and the decisions on the allocation of subjects to analysis sets will be made at latest at the RPM/DBLM.

Table 6.3: 1 Subject sets analysed

Class of endpoint	Subject set	
	TS	PKS
Disposition	X	
Exposure	X	
IPVs	X	
Demographic/baseline endpoints	X	
Other safety parameters	X	
PK endpoints		X

### **6.4 SUBGROUPS**

A subgroup analysis is not planned.

### **6.5 POOLING OF CENTRES**

This section is not applicable, because the study was performed in only one centre.

### **6.6 HANDLING OF MISSING DATA AND OUTLIERS**

**CTP:** If a subject is removed from or withdraws from the trial prior to first administration of trial medication, the data of this subject will not be entered in the case report form (CRF) or trial database and will not be reported in the clinical trial report (CTR). If a subject is removed from or withdraws from the trial after first administration of trial medication, this will be documented and the reason for discontinuation must be recorded in the CRF. In this case, the data will be included in the CRF/trial database and will be reported in the CTR.

**CTP:** *With respect to safety evaluations, it is not planned to impute missing values.*

The only exceptions where imputation might be necessary for safety evaluation are AE dates. Missing or incomplete AE dates are imputed according to BI standards (see 001-MCG-156\_RD-01 ([4](#))).

Missing data and outliers of PK data are handled according to BI standards (see 001-MCS-36-472\_RD-01) ([5](#)). **CTP:** *Drug concentration data identified with NOS (no sample available), NOR (no valid result), NOA (not analysed), BLQ (below the lower limit of quantification), or NOP (no peak detectable) will be displayed as such and not replaced by zero at any time point (this rule also applies also to the lag phase, including the predose values).*

**CTP:** *For the non-compartmental analysis, concentration data identified with NOS, NOR or NOA will generally not be considered. Concentration values in the lag phase identified as BLQ or NOP will be set to zero. All other BLQ/NOP values of the profile will be ignored. The lag phase is defined as the period between time zero and the first time point with a concentration above the quantification limit.*

## **6.7 BASELINE, TIME WINDOWS AND CALCULATED VISITS**

For safety measurements baseline is defined as the last measurement before study drug administration.

Time windows are defined in Section 6.1 of the CTP. Adherence to time windows will be checked at the RPM/DBLM.

## **7. PLANNED ANALYSIS**

The format of the listings and tables will follow the BI guideline "Reporting of clinical trials and project summaries" (001-MCG-159) ([10](#)).

The individual values of all subjects will be listed. Listings will generally be sorted by treatment group, subject number and visit (if visit is applicable in the respective listing). AE listings will be sorted by assigned analysis phase (see [Table 6.1: 1](#) for a definition of analysis phases). The listings will be contained in Appendix 16.2 (SDL) of the CTR.

The following standard descriptive statistical parameters will be displayed in summary tables of continuous variables:

N	number of non-missing observations
Mean	arithmetic mean
SD	standard deviation
Min	minimum
Median	median
Max	maximum

For plasma concentrations as well as for all PK parameters, the following descriptive statistics will additionally be calculated:

CV	arithmetic coefficient of variation
gMean	geometric mean
gCV	geometric coefficient of variation

The data format for descriptive statistics of plasma concentrations will be identical with the data format of the respective concentrations. The descriptive statistics of PK parameters will be calculated using the individual values with the number of decimal places as provided by the evaluation program. Then the individual values as well as the descriptive statistics will be reported with three significant digits in the CTR.

Tabulations of frequencies for categorical data will include all possible categories and will display the number of observations in a category as well as the percentage (%) relative to the respective treatment. Percentages will be rounded to one decimal place. The category missing will be displayed if and only if there actually are missing values. Percentages will be based on all subjects in the respective subject set whether they have non-missing values or not.

### **7.1 DEMOGRAPHIC AND OTHER BASELINE CHARACTERISTICS**

Only descriptive statistics are planned for this section of the CTR.

### **7.2 CONCOMITANT DISEASES AND MEDICATION**

Concomitant diseases will be coded according to the most recent version of MedDRA. Concomitant medication will be coded according to the most recent version of the World Health Organisation – Drug Dictionary.

Only descriptive statistics are planned for this section of the CTR.

A medication will be considered concomitant to a treatment, if it

- is ongoing at the time of administration of the respective treatment or
- starts within the analysis phase of the respective treatment (see [Section 6.1](#) for a definition of treatments and analysis phases).

### **7.3 TREATMENT COMPLIANCE**

Treatment compliance will not be analysed as a specific endpoint, but will be assessed for the treatment group receiving BI 655130 intravenously based on the duration of infusions (descriptive statistics of duration) and dose per infusion (descriptive statistics of the administered dose per infusion). Any deviations from complete intake will be addressed in the RPM/DBLM (cf. [Section 6.2](#)) and described in the CTR.

### **7.4 PRIMARY ENDPOINTS**

Analysis of relative BA of primary endpoints  $AUC_{0-tz}$  and  $C_{max}$  of BI 655130 in plasma will be performed as defined in Sections 7.1.3 and 7.3.1 of the CTP.

The statistical model for the primary analysis (comparison of subcutaneous versus intravenous administration of [redacted] of BI 655130) is an ANOVA model on the logarithmic scale including an effect for "treatment group" as defined in Sections 7.1.3 and 7.3.1 of the CTP.

Primary PK endpoints will also be assessed descriptively. The analysis of standard PK parameters is performed according to BI standards ([5](#)) [001-MCS-36-472\_RD-01].

